## **Appendix G: Whole Body Itch Numeric Rating Scale (NRS)**

ITCH NUMERIC RATING SCALE

Please rate the itching severity due to your psoriasis by circling the number that best describes your worst level of itching in the past 24 hours.

0 1 2 3 4 5 6 7 8 9 10

0 = No itching 10 = Worst itch imaginable

Naegeli, 2015.

# Appendix H: The Dermatology Life Quality Index (DLQI)

The aim of this questionnaire is to measure how much your skin problem has affected your life OVER THE LAST WEEK. Please check one box for each question.

1.	Over the last week, how itchy , sore , painful or stinging has your skin been?	_ Very much _ A lot _ A little _ Not at all	
2.	Over the last week, how embarrassed or self conscious have you been because of your skin?	_ Very much _ A lot _ A little _ Not at all	
3.	Over the last week, how much has your skin interfered with you going shopping or looking after your home or yard ?	_ Very much _ A lot _ A little _ Not at all	_ Not relevant
4.	Over the last week, how much has your skin influenced the clothes you wear?	_ Very much _ A lot _ A little _ Not at all	_ Not relevant
5.	Over the last week, how much has your skin affected any social or leisure activities?	_ Very much _ A lot _ A little _ Not at all	_ Not relevant
6.	Over the last week, how much has your skin made it difficult for you to do any sport ?	_ Very much _ A lot _ A little _ Not at all	_ Not relevant
7.	Over the last week, has your skin prevented you from working or studying?	_ Yes _ No	_ Not relevant
	If "No", over the last week how much has your skin been a problem at work or studying ?	_ A lot _ A little _ Not at all	
8.	Over the last week, how much has your skin created problems with your partner or any of your close friends or relatives ?	_ Very much _ A lot _ A little _ Not at all	_ Not relevant
9.	Over the last week, how much has your skin caused any sexual difficulties?	_ Very much _ A lot _ A little _ Not at all	_ Not relevant
10.	Over the last week, how much of a problem has the treatment for your skin been, for example, by making your home messy, or by taking up time?	_ Very much _ A lot _ A little _ Not at all	_ Not relevant

Finlay, 1994.

# **Appendix I:Titration Blister Card Configuration**

30mg BID	Titration and Trea	tment Card (	28 day +5 Extra)	
	1 1 10 1 200	30p	1 1 200	30p
	2 10 200	30p	2 10 200	30p
	3 10 200	30p	3 1	(30p)
	4 100 20	30p	4 100 20	(30p)
	5 100 20	30p	5 000 200	30
	6	30	6	30
	7	30	7	30
	8	30	8	30
	9	30	9	(30)
	10	30	10	30
	11	30	11	30
	12	30	12	30 30
	13	30	13	30
	14	30	14	30
	15	30	15	30
	16	30	16	30
	17	30	17	30
	18	30	18	30
	19	30	19	30
	20	30	20	(30)
	21	30	21	30
	22	30	22	(30)
	23	30	23	30
	24	30	24	30
	25	30	25	30
	26	30	26	30
	27	30	27	30
	28	30	28	30
	29	30	29	30
	30	30	30	30
	31	(30)	31	30
	32	30	32	30
	33	30	33	30
a a a				

**Appendix J: Active Treatment Dummy Titration Blister Card Configuration** 

30mg BID Dummy	Titration Card (2	8 day +5 Extra)	
1 1	(20p) (30)	1 1 200	30
2	20p 30	2 100 200	
3 100	20p 30	3 100 200	30
4 100	20p 30	4 100 200	30
5	20p 30	5 🐠 200	30
6	30	6	30
7	30	7	30
8	30	8	30
9	30	9	(30)
10	30	10	30
11	30	11	30
12	30	12	30
13	30	13	30
14	30	14	30
15	30	15	30
16	30	16	30
17	30	17	30
18	30	18	30
19	30	19	30
20	30	20	30
21	30	21	30
22	30	22	30
23	30	23	30
24	30	24	30
25	30	25	30
26	30	26	30
27	30	27	30
28	30	28	30
29	30	29	30
30	30	30	30
31	(30)	31	(30)
32	30	32	30
33	30	33	30

# **Appendix K: Placebo Treatment Blister Card Configuration**

Placeb	o Titration and Trea	tment Card (	28 day +5 Extra)	
	1 1 100	30p	1 1 200	(30p)
	2 100 200	30p	2 100 200	30 p
	3 100 200	(30p)	3 000 200	(30p)
	4 100 200	30p	4 100 200	(30p)
	5 100 200	30p	5 000 200	(30p)
	6	30p	6	30p
	7	30p	7	30p
	8	30p	8	30p
	9	30p	9	30p
	10	30p	10	30p
	11	30p	11	30p
	12	30p	12	30p
	13	30p	13	(30p)
	14	30p	14	(30p)
	15	30p	15	30p
	16	30p	16	30p
	17	30p	17	30p
	18	30p	18	30p
	19	300	19	30p
	20	30p	20	30p
	21	30p	21	30p
	22	30p	22	(30p)
	23	30p	23	(30p)
	24	(30p)	24	(30p)
	25	(30p)	25	(30p)
	26	(30p)	26	(30p)
	27	(30p)	27	30p
	28	30p	28	30p
	29	(30p)	29	30p
	30	30p)	30	30p
	31	30p	31	30p
	32	30p	32	30p
	33	30p	33	30p
Į.				

#### 1. JUSTIFICATION FOR AMENDMENT

Changes included in this amendment are summarized below:

- Provided clarification to Sections 6.1, 6.2 and 6.5
- Provided clarification to Sections 5 and 6.5 Safety Assessments, Serum and Urine Pregnancy Tests for Females of Childbearing Potential to further specify that an unscheduled serum pregnancy test should be performed if the FCBP subject has missed a menstrual period or has a positive urine dipstick test.
- Modified Sections 4.3, 5, 6.1, and 6.5 to include hepatitis C testing to be consistent with apremilast historical studies.
- Modified Section 10 Adverse Events to reflect the process by which adverse events are to be reported.

#### 1. JUSTIFICATION FOR AMENDMENT

Changes included in this amendment are summarized below:

- In the Protocol Summary, provided clarifications regarding the approximate enrollment limits in Study Design and topical psoriasis preparations in Study Population; included Columbia Suicide Severity Rating Scale (C-SSRS) in Overview of Key Safety Assessment and tipping point analysis in Statistical Method based on FDA recommendation.
- Provided clarification in Section 3.1 regarding the approximate enrollment limits as determined by baseline sPGA scores of mild (2) or moderate (3).
- Provided clarification in Section 4.2 Inclusion Criteria #6 to define topical psoriasis preparations.
- Modified Section 5 Table of Events to include Optional Consent for Research based on new protocol template; to include C-SSRS, additional body weight measures, additional clinical laboratory evaluations, and urine pregnancy tests based on FDA recommendations; and to include clarifications on the footnotes.
- Modified Sections 5, 6.1, and 6.3.2 to update the NAPSI assessment schedule.
- Provided clarification in Section 6 Procedures under Medical and Disease History to remove psoriatic arthritis. Clarified the need for subjects to sign optional consents for research before any sub-study sampling may be performed.
- Modified Section 6.1 to include options consents for research being presented to subjects, and to review prior/concomitant medications during the screening period.
- Modified Sections 6.1, 6.2, 6.3, 6.5, 17, Appendix A, and Appendix F to reflect the addition of C-SSRS based on FDA recommendation.
- Modified Section 6.5 with additional time points for urine pregnancy testing for FCBP subjects.
- Provided clarification in Section 6.7 to reflect the sub-studies are optional.
- Modified reference in Sections 6.8, 7.2 to reflect the addition of C-SSRS as an appendix.
- Provided modification in Section 7.7 investigational Product Compliance to include upper range of > 120% compliance between visits as meeting definition of a gross compliance problem.
- Provided clarification in Section 9.6.1.1 Primary Efficacy Endpoint where reference to LOCF was replaced with "tipping point analysis" based on FDA recommendation.
- Provided clarification in Section 11.1 Treatment Discontinuation to include the following reason: "Subjects with BMI < 18.5 kg/m2 at baseline who lose ≥ 5% of their baseline weight, based on FDA recommendation.
- Provided clarification to Appendix E to include a count of the number of nails with psoriasis involvement.
- Appendices F, G, H, I, J were modified to reflect the addition of C-SSRS as an appendix.

1. LIST OF ABBREVIATIONS

Table 1: Abbreviations and Specialist Terms

AE	Adverse Event
ANCOVA	Analysis of Covariance (model)
ATC	Anatomical-Therapeutic-Chemical
BID	Twice Daily
BMI	Body Mass Index
BSA	Body Surface Area (%) Affected by Psoriasis
CI	Confidence Interval
СМН	Cochran-Mantel-Haenszel
CRF or eCRF	(electronic) Case Report Form
CRO	Contract Research Organization
CRP	Clinical Research Physician
CSR	Clinical Study Report
C-SSRS	Columbia-Suicide Severity Rating Scale
DAO	Data As Observed
DLQI	Dermatological Life Quality Index
EAIR	Exposure Adjusted Incidence Rate
HRQoL	Health-Related Quality of Life
IP	Investigational Product
IRT	Interactive Response Technology
ITT	Intent-to-Treat
LS Mean	Least Squares Mean
MCMC	Markov Chain Monte Carlo
MedDRA	Medical Dictionary for Regulatory Activities
MI	Multiple Imputation
MMRM	Mixed-effect Model for Repeated Measures
	- Control of the cont

NRI	Non-responder Imputation
NRS	Numeric Rating Scale
PASI	Psoriasis Area and Severity Index
PD	Pharmacodynamic
PG	Pharmacogenetic
PK	Pharmacokinetic
PP	Per-Protocol (population)
PT	Preferred Term
REML	Restricted Maximum Likelihood
RNA	Ribonucleic Acid
SAE	Serious Adverse Event
SAP	Statistical Analysis Plan
ScPGA	Scalp Physician Global Assessment
SD	Standard Deviation
SE	Standard Error
SI	Standard International (unit)
sPGA	Static Physician Global Assessment
SOC	System Organ Class
TEAE	Treatment-emergent Adverse Event
USA	United States of America
WHODD	World Health Organization Drug Dictionary

2. INTRODUCTION

This statistical analysis plan (SAP) describes the analyses and data presentations for Celgene's protocol CC-10004-PSOR-022, "A phase 3, multi-center, randomized, double-blind, placebo-controlled study to evaluate the efficacy and safety of apremilast (CC-10004) in subjects with mild to moderate plaque psoriasis".

After all subjects have completed or have been discontinued from the Double-blind Placebo-controlled Phase (Weeks 0 to 16), a Week 16 database restriction will be performed; the primary data analysis will be conducted and a Week 16 Clinical Study Report will be generated. No interim analysis is planned prior to this primary data analysis. At the end of the study, after all subjects have completed or have been discontinued from the Apremilast Extension Phase (Weeks 16 to 32) and the Observational Follow-up Phase, the final database lock and analysis will be performed and the final Clinical Study Report (CSR) will be generated.

No pharmacokinetic (PK) analyses will be done for this study. The details of the pharmacodynamic (PD) analyses except biomarker analysis for plasma proteins assessments will be specified in a separate PD analysis plan.

This SAP provides a more technical and detailed elaboration of the statistical analyses as outlined and/or specified in the study protocol amendment 2 dated 21Nov2018. The SAP will be finalized and signed prior to the unblinding of the Week 16 database. All statistical analyses detailed in this SAP will be conducted using SAS® Version 9.3 or higher.

3. STUDY OBJECTIVES STUDY OBJECTIVES

3.1. Primary Objective

• To evaluate the clinical efficacy of oral apremilast 30 mg twice daily (BID), compared to placebo, in subjects with mild to moderate plaque psoriasis during the 16-week Placebo-controlled Phase

3.2. Secondary Objectives

The secondary objectives are:

- To evaluate the safety and tolerability of apremilast 30 mg BID, compared with placebo, in subjects with mild to moderate plaque psoriasis
- To evaluate the effect of apremilast 30 mg BID compared with placebo on itch over the whole body caused by plaque psoriasis
- To evaluate the effect of apremilast 30 mg BID compared with placebo on Health-related Quality of Life (HRQoL)

3.3. Exploratory Objectives

4. INVESTIGATIONAL PLAN

4.1. Overall Study Design and Plan

This is a Phase 3, multicenter, randomized, placebo-controlled, double-blind study designed to evaluate the efficacy and safety of apremilast (CC-10004) in subject with mild to moderate plaque psoriasis.

Approximately 574 subjects will be enrolled and randomized 1:1 to receive either apremilast 30 mg BID or placebo for the first 16 weeks. Subjects will be randomized based on a permuted block randomization using a centralized Interactive Response Technology (IRT). Randomization to apremilast arm or placebo arm will be stratified by baseline Static Physician Global Assessment (sPGA) score (mild [2] or moderate [3]). Approximately 30% of subjects with mild plaque psoriasis will be enrolled in the study.

[figure not shown]
- Subjects randomized to the apremilast 30 mg BID treatment group will receive apremilast 30 mg tablets orally twice daily for the first 16 weeks
- Subjects randomized to the placebo treatment group will receive placebo tablets (identical in appearance to apremilast 30 mg tablets) orally twice daily for the first 16 weeks
- All subjects will receive apremilast 30 mg tablets orally twice daily after the Week 16 Visit through the end of the Apremilast Extension Phase of the study

The study will consist of four phases (Figure 1):

- Screening Phase up to 35 days
- Double-blind Placebo-controlled Phase Weeks 0-16
 - Subjects will be randomly assigned in a 1:1 ratio to either apremilast 30 mg BID or placebo.
- Apremilast Extension Phase Weeks 16-32
 - All subjects will be switched to (or continue with) apremilast 30 mg BID. All subjects will maintain this dosing through Week 32.
- Observational Follow-up Phase 4 weeks
 - Four-week Post-Treatment Observational Follow-up Phase for all subjects who complete the study or discontinue the study early

After all subjects have completed the Week 16 Visit (or discontinued from the study), a Week 16 database restriction will be performed; the primary data analysis will be conducted and a Week 16 Clinical Study Report (CSR) will be generated. However, unblinded data will only be made available to select Sponsor and Contract Research Organization (CRO) team members involved with analysis of the data and preparation of the Week 16 CSR. All other Sponsor, site, and CRO personnel directly involved with the conduct of the study, will remain blinded to treatment assignments until the final database lock at the conclusion of the study.

Figure 1: Study Design

4.2. Study Endpoints

The endpoints of the study are listed below.

4.2.1. Primary Endpoint

• Static PGA (sPGA) 0/1: Proportion of subjects with an sPGA score of clear (0) or almost clear (1) with at least a 2-point reduction from baseline at Week 16

4.2.2. Secondary Endpoints

- BSA-75: Proportion of subjects who improved ≥ 75% in BSA (BSA-75) from baseline at Week 16
- BSA: Change from baseline in affected BSA at Week 16
- PASI: Change from baseline in total PASI score at Week 16
- BSA ≤ 3%: Proportion of subjects who achieved BSA ≤ 3% for subjects with baseline BSA > 3% at Week 16
- Itch NRS: Proportion of subjects with ≥4-point reduction (improvement) from baseline in the whole body itch NRS score at Week 16, among subjects with baseline whole body itch NRS ≥ 4
- ScPGA: Proportion of subjects with ScPGA score of clear (0) or almost clear (1) with at least a 2-point reduction from baseline at Week 16, among subjects with baseline ScPGA score ≥ 2
- DLQI: Change from baseline in DLQI total score at Week 16

4.2.3. Exploratory Efficacy Endpoints

4.2.4. Exploratory Pharmacokinetic Endpoints

Not applicable.

4.2.5. Exploratory Pharmacodynamics Endpoints

4.2.6. Safety Endpoints

Safety endpoints will include:

- Adverse events (AEs): Type, frequency, severity, seriousness, and relationship of AEs to IP
- Death
- Clinical laboratory evaluations
- Vital signs and weight
- Columbia Suicide Severity Rating Scale (C-SSRS)

4.2.7. Derivations of Efficacy Endpoints

The derivation of efficacy endpoints is described below in separate sections. Baseline definition for all efficacy endpoints is given in Section 5.3. Change from baseline is calculated as post-baseline visit value minus the baseline value. Percent change from baseline is defined as 100* Change from baseline/Baseline value (%). Handling of time points is described in Section 5.4.

4.2.7.1. Static Physician Global Assessment (sPGA)

The sPGA is the assessment of whole body psoriasis by the investigator of the overall disease severity at the time of evaluation. The sPGA is a 5-point scale ranging from clear (0), almost

clear (1), mild (2), moderate (3), to severe (4), incorporating an assessment of the severity of the three primary signs of the disease: erythema, scaling and plaque elevation.

The sPGA response at a post-baseline visit is defined as achieving sPGA score of clear (0) or almost clear (1) with at least a 2-point reduction from baseline.

4.2.7.2. Body Surface Area (BSA)

BSA is a measurement of involved skin over the whole body. The overall BSA affected by psoriasis is estimated based on the palm area of the subject's hand. The surface area of the whole body is made up of approximately 100 palms or "handprints" (each entire palmar surface or "handprint" equates to approximately 1% of total body surface area).

BSA scores will be presented with one digit after the decimal point. For post-baseline visits, BSA score change and percent change from baseline will be derived. BSA score percent change will be rounded to integers.

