6.2. Multiplicity Adjustment

The primary and secondary efficacy endpoints will be hierarchically ranked for testing to control the overall type I error rate in claiming statistical significance at the two-sided 0.05 significance level. Specifically, for the primary efficacy endpoint (sPGA response at Week 16), if the two-sided p-value from the comparison between apremilast arm and placebo arm is below 0.05, the outcome will be considered statistically significant and apremilast will be declared effective. For any secondary endpoint, statistical significance will be claimed only if its two-sided p-value is below 0.05 and tests for the primary endpoint and all previous secondary endpoints are significant at the two-sided 0.05 level. The proposed test sequence for the primary and secondary efficacy endpoints is listed as the following:

- Proportion of subjects with an sPGA score of clear (0) or almost clear (1) with at least a 2-point reduction from baseline at Week 16
- Proportion of subjects who improved $\geq 75\%$ in BSA (BSA-75) from baseline at Week 16
- Change from baseline in affected BSA at Week 16
- Change from baseline in total PASI score at Week 16
- Proportion of subjects who achieved BSA ≤ 3% for subjects with baseline BSA > 3% at Week 16
- Proportion of subjects with ≥4-point reduction (improvement) from baseline in the whole body itch NRS score at Week 16, among subjects with baseline whole body itch NRS ≥ 4

- Proportion of subjects with ScPGA score of clear (0) or almost clear (1) with at least a 2-point reduction from baseline at Week 16, among subjects with baseline ScPGA score ≥2
- Change from baseline in DLQI total score at Week 16

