6.4.1. Binary Variables

The binary variables for secondary endpoints include the following:

- Proportion of subjects who improved ≥ 75% in BSA (BSA-75) from baseline at Week
 16
- Proportion of subjects who achieved BSA ≤ 3% for subjects with baseline BSA > 3% at Week 16
- Proportion of subjects with ≥4-point reduction (improvement) from baseline in the whole body itch NRS score at Week 16, among subjects with baseline whole body itch NRS ≥ 4
- Proportion of subjects with ScPGA score of clear (0) or almost clear (1) with at least a 2-point reduction from baseline at Week 16, among subjects with baseline ScPGA score > 2

For these binary endpoints, the treatment difference between apremilast arm and placebo arm will be compared using CMH test adjusting for the stratification factor at randomization. The two-sided p-values from the CMH test, the adjusted treatment difference in proportion using the weighted average of the treatment differences across the strata with the CMH weights, along with the associated two-sided 95% CIs using a normal approximation to the weighted average will be provided.

Missing values will be imputed using the similar MI method as the primary endpoint, with sensitivity analysis using the NRI method as described in section 6.3.

Further, analyses of the following secondary endpoints will be performed for the subjects with baseline sPGA = 2 (mild psoriasis) and sPGA = 3 (moderate psoriasis):

- Proportion of subjects who improved ≥ 75% in BSA (BSA-75) from baseline at Week
 16
- Proportion of subjects who achieved BSA ≤ 3% for subjects with baseline BSA > 3% at Week 16
- Proportion of subjects who achieved BSA ≤ 1% for subjects with baseline BSA > 1% at Week 16

The treatment difference between apremilast arm and placebo arm will be compared using Chi-squared test. The two-sided p-values from the Chi-squared test, the treatment difference in proportion, along with the associated two-sided 95% CIs will be provided.

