APPENDIX A3– REPORTING CONVENTIONS

- Statistical test of the treatment difference will use two-sided significance level 0.05 for significance or nominal significance.
- P-values will be rounded to 4 decimal places. p-values that round to 0.0000 will be presented as '<0.0001' and p-values that round to 1.000 will be presented as '>0.9999';
- Confidence intervals (CIs) will be presented as two-sided 95% CIs unless specified differently in specific analysis;
- Summary statistics will consist of the number and percentage of subjects in each category for discrete variables, the sample size, mean, median, standard deviation (SD), minimum, and maximum for continuous variables, the 25th (Q1) and 75th (Q3) percentiles will also be applied to efficacy continuous variables;
- Mean and median values will be formatted to one more decimal place than the
 measured value. Standard deviation values will be formatted to two more decimal
 places than the measured value. Minimum and maximum values will be presented to
 the same number of decimal places as the measured value;
- Percentages will be rounded to one decimal place. The number and percentage of responses will be presented in the form xx (xx.x), where the percentage is in the parentheses;
- Analysis and summary tables will have the analysis population sample size (i.e., number of subjects) in the column header;
- Subject data listings will be provided to support the tables and graphs. Listings will be sorted for presentation in order of subject number and date of procedure or event.

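### Does integer rounding of BSA percent change let subjects below 75% improvement count as BSA-75 responders?

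*SAP*

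**What the plan says.** SAP section 4.2.7 gives the formula: "Percent change from baseline is defined as 100* Change from baseline/Baseline value". It has no rounding step. Section 4.2.7.2 then deals with precision. It says "BSA scores will be presented with one digit after the decimal point", notes that change and percent change are derived, and ends with "BSA score percent change will be rounded to integers". It does not mention BSA-75, a responder flag or a 75% cut.

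The endpoint is stated in section 4.2.2 as "Proportion of subjects who improved ≥ 75% in BSA (BSA-75) from baseline at Week 16", and sections 6.2 and 6.4.1 repeat it in nearly the same words. In section 6.2 it comes directly after the primary endpoint. A later endpoint can be claimed only if "tests for the primary endpoint and all previous secondary endpoints are significant at the two-sided 0.05 level", so BSA-75 gates the six endpoints listed after it.

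For missing data, section 6.4.1 says "Missing values will be imputed using the similar MI method as the primary endpoint". Appendix A3 adds a display rule, "Percentages will be rounded to one decimal place", which does not bear on the 75% cut.

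**The concern.** The rounding sentence sits under the derivations of efficacy endpoints and carries no exception for the 75% cut. The sPGA, itch NRS and ScPGA subsections each define response; the BSA subsection does not. A programmer who works down the section in order could create an integer percent change and then apply the cut to it. The working cut would become 74.5%. A subject going from 7.5% to 1.9% has improved by 74.67%, would be stored as 75, and would count as a responder without meeting the endpoint.

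The shift goes one way, because a true improvement of 75% or more never rounds below 75. Two programmers could also obtain different counts from the same text, on the endpoint that opens the secondary hierarchy.

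**Working it through.** **Plan's own figure.** The documents give no rate or power for BSA-75. The only design figure is power above 90% for the primary endpoint, at 15% versus 30%. With 20% dropout, 287 × 0.8 = 229 per arm (rounded down). For the pooled chi-square test:

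z = [0.15 × √229 − 1.96 × √(2 × 0.225 × 0.775)] / √(0.15 × 0.85 + 0.30 × 0.70) = (2.270 − 1.157) / 0.581 = 1.915

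This is power of 97.2%. The stated figure holds and does not depend on BSA rounding.

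**Which values can change status.** Inputs: baseline BSA b from 2% to 15% (Protocol section 4.2, criterion 5); Week 16 BSA p; improvement = 100 × (b − p)/b. Status changes only if improvement is at least 74.5% and below 75%, which is 0.25b < p ≤ 0.255b. The window is 0.005b wide.

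If BSA is recorded in steps of s, then b and p are multiples of s, and p − 0.25b is a multiple of s/4. The smallest possible excess above 0.25b is therefore s/4. A pair can fall in the window only if s/4 ≤ 0.005b, that is b ≥ 50s. A count of every pair with baseline 2 to 15 agrees:

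| Recording step s | Needs b of at least (50s) | Pairs that change status | Lowest baseline reached |
|---|---|---|---|
| 0.1 | 5 | 38 (one for each of 38 of 131 possible baselines) | 5.1 |
| 0.25 | 12.5 | 3 | 12.75 |
| 0.5 | 25 (outside entry range) | 0 | none |
| 1.0 | 50 (outside entry range) | 0 | none |

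On the 0.1 grid the affected improvements run from 74.51% (5.1 to 1.3) to 74.83% (14.7 to 3.7).

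**How many subjects.** The documents give no distribution of BSA change, so this needs an assumption. Simulations on the 0.1 grid under three assumed response distributions put 0.17%, 0.32% and 0.35% of subjects in the window. That is 287 × 0.0017 = 0.5 to 287 × 0.0035 = 1.0 per arm. A wider assumed range of 0% to 1% gives 0 to 2.9 per arm.

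**Effect on the test.** Assumed counts, 287 per arm, unstratified chi-square = (difference in proportions)² / [2 × p̄(1 − p̄)/287]:

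- 60 versus 41: p̄ = 101/574 = 0.1760; (19/287)² / (2 × 0.1450/287) = 4.34, p = 0.037.
- 61 versus 42 (one responder added to each arm): p̄ = 103/574 = 0.1794; the same difference gives 4.27, p = 0.039.
- 86 versus 43 (about 30% and 15%): p is near 0.00002, and one more responder per arm leaves it there.

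**Imputed values.** Section 6.3 uses MCMC only to make the missing pattern monotone, then fills what remains by predictive mean matching. Week 16 is the last visit in the sequence, so a missing Week 16 value is never an interior gap and is filled at the matching step, which draws values observed in other subjects. If the similar method for BSA keeps these two steps, imputed Week 16 BSA lies on the recording grid and the table applies to it too.

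**The case for a change.** The strongest case for acting is that the text separates presenting from rounding. Scores are said to be presented to one decimal, whereas percent change is derived and rounded. Display formats have their own place in Appendix A3, which suggests that the integer rule acts on the stored variable. Recording to 0.1 is also plausible: the PASI form in Protocol Appendix C adds hand counts over four regions to a total BSA and asks for calculations to one decimal. A gatekeeping flag should have one reproducible definition before the Week 16 unblinding, and one sentence would supply it.

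Some of this stands. The order of derivation is not written down, and the documents do not settle the recording precision. The misclassification itself is an inference, though. No text says the flag comes from the rounded value, and the endpoint wording taken alone excludes every affected subject. The same rounding sentence appears for PASI in section 4.2.7.3, where the secondary endpoint is absolute change and has no percent cut, so it reads as a stock precision convention. BSA is estimated in palms of about 1% each, so coarser recording, with no effect at all, is at least as plausible as recording to 0.1.

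The one-way shift is not a bias between arms. A common 74.5% cut would apply to both blinded groups and would still give a valid test of no difference, so the fixed sequence keeps its error control. A result lying exactly at the significance boundary could turn on a single subject, but that is true of any responder cut.

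**Conclusion.** This is a gap in wording that analysts fill sensibly, and no change is called for. The natural programming of BSA-75 compares unrounded improvement with 75%, or equivalently Week 16 BSA with one quarter of baseline, because that is what the endpoint and the formula say. If the rounded value were used instead, the consequence would be about 0 to 1 extra responder per arm of 287, in either arm. That size rests on recording to 0.1 and on assumed response distributions; with half- or whole-palm recording it is exactly zero. Sample size, primary power and type I error are unaffected, and the conclusion on BSA-75 and the endpoints after it would be sound under either reading.
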